Eight of the disease groups will include subjects with 1) symptomatic human immunodeficiency virus (HIV)/acquired immunodeficiency syndrome (AIDS); 2) solid malignancy; 3) bone marrow transplant; 4) organ transplant (excluding bone marrow); 5) rheumatologic or other inflammatory condition; 6) a primary immunodeficiency; 7) other immune conditions; and 8) chronic kidney disease (CKD) or end stage renal disease (ESRD). Subjects in these IC groups (shown as “Group 1” in [Figure 1](#)) will be further stratified by treatment status: those with usage of immunosuppressive medications for >14 days anytime during the baseline period and those without any evidence of >14 days of usage of an immunosuppressive medication during the baseline period. Subjects with a bone marrow or

organ transplant will be further stratified by those who received their 1st vaccine dose >100 days prior to their transplant and those who received it <100 days prior to their transplant. Subjects with a solid malignancy will be further stratified by their treatment type: chemotherapy or radiation therapy or immunomodulator, or a mix of these treatments.

The 9th subject group (shown as “Group 2” in [Figure 1](#)) will include those with a hematologic malignancy, required to have usage of an immunosuppressive medication (chemotherapeutic agent, immunomodulator, or systemic corticosteroid) for >14 days anytime during the baseline period; this subject group will be further stratified by their use of an immunosuppressive medication >6 months or ≤ 6 months prior to their index date.

The 10th subject group will include subjects with usage of an immunosuppressive medication (chemotherapeutic agent, immunomodulator, or systemic corticosteroid excluding low-dose [<60mg/day] prednisone) for >14 days anytime during the baseline period, but without any ICD-10-CM diagnosis codes indicating the above listed IC conditions on a healthcare claim anytime during the baseline period. Subjects with >14 days usage of antimetabolites anytime during the baseline period will be excluded from this subject group and placed in the 11th subject group.

[figure not shown]

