This algorithm differs from that used in Greenberg et al²⁶ by the following modifications, considered relevant for COVID-19 based on expert medical opinion: the inclusion of subjects with a solid malignancy who had radiation therapy or any treatment mix; the separation of subjects with a bone marrow transplant and those with an organ transplant; the inclusion of chronic inflammatory demyelinating polyneuropathy and immune thrombocytopenic purpura in the “rheumatologic or other inflammatory condition” group; the inclusion of sickle cell disease, asplenia, and psoriatic arthritis in the “other immune disorders” group; the addition of subjects with primary immunodeficiencies and those with CKD or ESRD; the requirement that subjects with a hematologic malignancy have evidence of usage of an immunosuppressive medication; the reclassification of subjects with only usage of an immunosuppressive medication; the removal of subjects with usage of only low dose prednisone; and the inclusion of an ad-hoc group of subjects who had taken anti-metabolites. Additionally, the following subcategories will be created: the first 9 subject groups were stratified according to treatment status; organ transplant subjects will be stratified according to time of receipt of the first COVID-19 vaccine dose in relation to the date of transplant; and subjects with hematologic malignancy will be stratified by time of receipt of treatment relative to their 1st vaccine dose.

When categorizing subjects with the different types of IC conditions, all the subject groups will be mutually exclusive. Subjects meeting the criteria for classification into only a single IC group will be classified accordingly into subject groups 1-11. Any subjects meeting the criteria for classification into multiple IC groups will be categorized into the >1 IC condition group (12th subject group).

All subjects will be grouped into an overall study population consisting of subjects identified as having an IC condition or not (i.e., non-IC). Subjects with an IC condition will be further categorized into the specific IC condition groups.

Figure 1: Algorithm to define immunocompromising conditions

Algorithm for case definitions of IC conditions in HealthVerity US claims database

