8.3. Variables

Table 1. Immunocompromising Conditions definition

Variable	Role	Data source(s)	Operational definition
Immunocompromising Conditions	Cohort Definition	HealthVerity Vaccine Data	
Subjects will be categorized into the following 12 mutually exclusive IC groups based on the algorithm detailed in Figure 1:
 
Symptomatic HIV/AIDS, solid malignancy, bone marrow transplant recipients, organ transplant recipients, rheumatologic or other inflammatory conditions, primary immunodeficiencies, other intrinsic immune conditions, chronic kidney disease or end stage renal disease, hematologic malignancy, immunosuppressive treatment only, antimetabolites only, or >1 IC condition.

PFIZER CONFIDENTIAL

Table 1. Immunocompromising Conditions definition

Variable	Role	Data source(s)	Operational definition
			
Subjects falling into more than one of these categories will be categorized as having >1 IC condition.
 
At a minimum, subjects will be required to have one inpatient claim or two outpatient claims on separate days with the IC condition of interest in the baseline period. In cases when >14 days of treatment are required it will be based on the dispensed day supply or distinct days of treatment in the baseline period.
 
The main diagnosis codes to identify IC conditions are presented in ANNEX 1. LIST OF STAND ALONE DOCUMENTS.

Table 2. Vaccination Status definitions

Variable	Role	Data source(s)	Operational definition
Any vaccination	Cohort Definition	HealthVerity Vaccine Data	
Patients with a claim for any vaccine will be considered vaccinated with any vaccine based on the following codes:
 
Pfizer/BioNTech: 91300, 0001A, 0002A, 59267100001, 59267100002, 59267100003
 
Moderna: 91301, 0011A, 0012A, 80777027310, 80777027399, 80777027315, 80777027398
 
Johnson & Johnson: 91303, 0031A, 59676058005, 59676058015
 
Source: https://www.cdc.gov/vaccines/programs/iis/COVID-19-related-codes.html

Fully Vaccinated	Cohort Definition	HealthVerity Vaccine Data	
Patients will be considered fully vaccinated if they meet any of the following definitions:
 
Two claims for Pfizer/BioNTech vaccine on separate days with >14 days of follow-up after the 2nd vaccination date. No claims for any other vaccines are allowed.

PFIZER CONFIDENTIAL

Table 2. Vaccination Status definitions

Variable	Role	Data source(s)	Operational definition

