ANNEX 3. ICD-10 CODE LIST

IC Condition	ICD-10 Code
HIV/AIDS*	B20-B24
Solid malignancy	
Organ/system malignant tumors	C00-C07; C11-C19; C22-C80; Z85
Neuroendocrine tumors	C7A; C7B; D3A
Neoplasms of uncertain behavior	D00-D49
Bone marrow transplant	Z94.81
Organ transplant	
Complications of transplanted organ	T86
Organ transplant status	Z94 except Z94.81; Z98.85
Rheumatologic or other inflammatory condition	
Sarcoidosis	D86
Amyloidosis Not Otherwise Specified (NOS)	E85
Familial Mediterranean fever	E85.0; M04
Amyloidosis Not Elsewhere Classified (NEC)	E85.1; E85.3; E85.8
Multiple sclerosis	G35
Other Central Nervous System (CNS) demyelination	G36; G37.1; G37.3; G37.8; G37.9
Acute infective polyneuritis	G61.0; G61.9
Acute myocarditis	I40
Polyarteritis nodosa and other	M30
Allergic alveolitis/pneumonitis NOS	T78.40; J67.9
Other alveolar pneumonopathy	J84.01; J84.02; J84.09

PFIZER CONFIDENTIAL

IC Condition	ICD-10 Code
Enteritis and colitis	K50-K52
Lupus erythematosus	L93.0; L93.2; M32
Diffuse connective tissue disease	L94; M35.8; M35.9
Arthropathy with infection	M12.9; M01.X0; M02.10
Crystal arthropathies	M11
Rheumatoid arthritis/inflammatory polyarthropathy	M05-M14
Inflammatory spondylopathies	M46
Polymyalgia rheumatica	M31.5; M35.3
Chronic inflammatory demyelinating polyneuropathy	G61.81
Immune thrombocytopenic purpura	D69.3
Primary Immunodeficiency	
X-linked agammaglobulinemia	D80.8
Common variable immunodeficiency	D83.1; D83.2; D83.8; D83.9
Immunoglobulin A (IgA) deficiency	D80.2
Immunoglobulin G (IgG) sub-class deficiency	D80.3
Severe combined immunodeficiency	D81.1
Di George syndrome	D82.1
Wiskott-Aldrich	D82.0
Ataxia telangiectasia	G11.3
Interferon-gamma/Interleukin 12 axis deficiencies	D84.89
Persistent complement, properdin or Factor B deficiency	D84.1
Received eculizumab for >14 days in the baseline period	
Chronic granulomatous disease	D71
Chediak-Higashi	E70.330
Leukocyte adhesion deficiency	D72: Genetic anomalies of leukocytes
Myeloperoxidase deficiency	D72.89: Other specific disorders of White Blood Cells (WBCs)

PFIZER CONFIDENTIAL

IC Condition	ICD-10 Code
Other immune conditions	
Disorders of immune mechanism	D89
Neutropenia	D70
Functional disorders of neutrophils	D71
Genetic anomalies of leukocytes	D72.0
Decreased leukocyte count	D72.81
Leukocyte disease NEC	D72.89
Leukocyte disease NOS	D72.9
Myelofibrosis	D75.81
Blood diseases NEC	D47.4; D75.89; D75.9; D89.2
Blood diseases NOS	D75.9; D75.89
Immunologic findings NEC	R76; R83.4-R87.4; R89.4

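### Annex 3 does not carry out the marrow/organ transplant split: the organ group excludes only Z94.81 from Z94 and nothing from T86

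*Combined protocol and SAP*

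**What the plan says.** Annex 3 has three relevant entries. The marrow entry is "Bone marrow transplant Z94.81", with no other code. The organ entry has a complications line, "Complications of transplanted organ T86", and a status line, "Z94 except Z94.81; Z98.85".

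Section 8.2.1 describes the fourth disease group as "organ transplant (excluding bone marrow", and the subgroup list in section 8.7 repeats that restriction. Section 8.2.1 also lists, among its modifications of the published algorithm, "the separation of subjects with a bone marrow transplant and those with an organ transplant".

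Two rules decide where a subject ends up. Table 1 (section 8.3) sets the claim count: "subjects will be required to have one inpatient claim or two outpatient claims on separate days with the IC condition of interest". Section 8.2.1 sets the overlap rule: "Any subjects meeting the criteria for classification into multiple IC groups will be categorized into the >1 IC condition group (12th subject group". Neither transplant group requires drug use for entry; more than 14 days of immunosuppressant use only stratifies these groups.

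Section 8.7 plans results for each IC condition, including screening-method VE by IC group.

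**The concern.** The text and the code list do not match. The text makes the split a deliberate design choice. The code list takes one status code out of the organ group's Z94 range and takes nothing out of T86. The marrow entry has no complication code at all, so no graft-complication claim can ever place a subject in the marrow group, whatever graft it concerns.

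The stake is in the condition-specific results. Each named transplant group supplies a breakthrough rate, a severity description and, in the exploratory aim, the PV and PCV from which VE is calculated. Both transplant groups are also stratified by the timing of the first dose relative to transplant, so a misfiled subject carries into those strata. The background section says the work should help show which IC conditions predispose to reduced VE, and that needs groups that hold what their labels say.

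**Working it through.** The plan states no figure on this point. The check applies the Annex 3 entries and the two rules literally.

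**From the documents alone.** Each line assumes that the claim count is met for each code named.

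- Z94.81 only: bone marrow.
- Any other Z94 code only, any T86 code only, or Z98.85 only: organ transplant.
- Z94.81 together with any other Z94 code, any T86 code or Z98.85: both groups are met, so the subject goes to the group with more than one IC condition.

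The claim count matters. A recipient with Z94.81 and a single outpatient T86 claim does not meet the organ group and stays in bone marrow. The second condition needs its own inpatient claim or two outpatient claims on separate days.

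**With subcode meanings added.** The following are assumptions from ICD-10-CM, the coding system the protocol specifies; they are not printed in the documents. Z94.84 is stem-cell transplant status, T86.0 is complications of marrow transplant, T86.5 is complications of stem-cell transplant, and Z94.0 is a solid-organ code.

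| Qualifying codes | As written | With Z94.84, T86.0x and T86.5 moved |
|---|---|---|
| Z94.81 | Bone marrow | Bone marrow/stem cell |
| Z94.84 | Organ | Bone marrow/stem cell |
| T86.0 or T86.5 | Organ | Bone marrow/stem cell |
| Z94.81 and Z94.84 | More than one condition | Bone marrow/stem cell |
| Z94.81 and T86.0 | More than one condition | Bone marrow/stem cell |
| Z94.0 | Organ | Organ |
| Z94.81 and qualifying hematologic malignancy | More than one condition | More than one condition |
| Z94.84 and qualifying hematologic malignancy | More than one condition | More than one condition |

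Rows 2 to 5 change; the others do not. Every change is between IC groups, so a subject who qualifies through either entry is in the IC cohort before and after. (One edge case is set aside. A subject with exactly one outpatient claim under each entry and no other IC condition would, on Table 1's per-condition count, meet neither group as written.)

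**Tissue grafts, a separate question.** On the further assumption that Z94.5 to Z94.7 are skin, bone and corneal graft status, a subject with only such a code is filed as organ transplant. If that is not intended, a subject with no other IC condition belongs in the non-IC cohort. The documents give no counts, so only the direction can be shown. Let f be the share of organ-group person-time from tissue grafts, assume they have the non-IC rate, and let k be the true organ versus non-IC rate ratio. Then

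observed ratio = (1 − f)k + f = 1 + (1 − f)(k − 1).

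- k = 2: f = 5%, 10%, 20%, 30% gives 1.95, 1.9, 1.8, 1.7.
- k = 3: the same shares give 2.9, 2.8, 2.6, 2.4.

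These values of f and k are illustrative.

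**The case against.** The strongest reply is that the subcode meanings come from outside the documents, Figure 1 is not available to read, and Table 1 calls the Annex codes the main ones, so the working list may differ. The plan also stratifies transplant recipients by immunosuppressant use, foresees sensitivity analyses that vary the IC case definition, and concedes in section 8.9 that the effect of its modifications on accuracy cannot be assessed. Condition-specific results are secondary and VE is exploratory.

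Part of this stands. The meanings must be labelled as an assumption, and the consequence is confined to subgroup results. The rest does not remove the problem. Extra marrow codes would not undo the organ entry's explicit capture of all T86 and the remaining Z94; the overlap would still trigger the more-than-one-condition rule. Treatment strata divide the organ group by drug use, not by graft type. A general promise of sensitivity analyses does not correct the main definition.

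Four stronger readings are tempting and are not supported:

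- That the marrow group keeps only uncomplicated recipients. The claim-count rule means one outpatient complication claim moves nobody.
- That a stated fraction of marrow recipients is lost. The documents give no code frequencies. Recipients who also qualify for hematologic malignancy go to the more-than-one-condition group under any split, and organ recipients who also meet the broad kidney code list leave the organ group too, so such losses cannot all be laid to the transplant codes.
- That neither group describes its label. The marrow group, defined by Z94.81, would be incomplete rather than contaminated, and nothing shows that solid-organ recipients are a minority of the organ group.
- That tissue-graft codes and Z98.85 are errors. Their inclusion is a case-definition choice and may be inherited from the published algorithm.

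**Conclusion.** The concern holds in a limited form. From the documents alone, the Annex 3 code ranges are not shown to deliver an organ group without marrow, and they can count one transplant as two conditions. Given the ICD-10-CM meanings of Z94.84, T86.0 and T86.5, literal application misfiles stem-cell recipients with those status codes, and recipients with qualifying complication claims, in the condition-specific incidence and VE results.

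The number affected cannot be derived from the documents. Recipients with only Z94.81 are filed correctly. The primary IC versus non-IC comparison is not affected by the marrow and stem-cell part. Only the tissue-graft question could place otherwise non-IC subjects in the IC cohort, and whether that is unintended is for the sponsor to say.

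**What to change.** In Annex 3, rename the marrow entry bone marrow/stem-cell transplant and give it Z94.81, Z94.84, T86.0x and T86.5, after checking these meanings in ICD-10-CM. Exclude the same codes from the organ entry's Z94 and T86 ranges, preferably by listing the subcodes of each group rather than whole categories.

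Separately, state whether the tissue-graft codes under Z94 and T86, and Z98.85, are meant to qualify as organ transplant. If they are kept, use the IC-case-definition sensitivity analysis already foreseen in section 8.7 to repeat the results without them.

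The cost is an edit to the transplant entries and a re-run, with no new data. The drawback is slightly less comparability with the published algorithm, which section 8.2.1 already modifies.

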8.2.1. Inclusion criteria

Patients must meet all of the following inclusion criteria to be eligible for inclusion in the study:

1. Unique enrollees in the HealthVerity Vaccine dataset any time **after** 10 December 2020
2. At least 12 years on the index date (ie, first vaccination date)
3. No evidence of prior COVID-19 infection (a medical claim, pharmacy claim, or chargemaster record with an International Classification of Diseases, 10th Revision, Clinical Modification (ICD-10-CM) diagnosis code of U07.1) in the 12 months prior to the index date
4. Have 12 months of continuous enrollment with medical benefits (with or without pharmacy benefits) prior to the index date

Subjects with an IC condition were identified via an algorithm originally developed and validated by Greenberg et al²⁴ for use in administrative claims database studies. For this study, this algorithm will be modified and expanded based on expert medical opinion. The algorithm is depicted in [Figure 1](#).

Subjects will be identified as immunocompromised if they had ≥ 1 hospitalization or ≥ 2 outpatient visits on separate dates with an ICD-10-CM code on a healthcare claim indicating an IC condition or if they had usage of specific immunosuppressive medications during the 12-month baseline period. The IC case definition will incorporate 8 groups based on clinical diagnoses only, 1 group based on both clinical diagnoses and usage of immunosuppressive medication, and 2 other groups based on usage of immunosuppressive medication only, for a total of 11 groups with an IC condition ([Figure 1](#)). Subjects with >1 IC condition will also be assessed, for a total of 12 mutually exclusive groups for inclusion in this study. The list of ICD-10-CM codes used to identify IC cases by diagnosis and list of immunosuppressive medications are shown in the Annex.

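### Annex 3's diagnosis-only rheumatologic/inflammatory group admits unspecified allergy, unspecified arthropathy and gout codes, which can dilute the IC versus non-IC contrast

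*Combined protocol and SAP*

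**What the plan says.** Section 8.2.1 of the protocol says subjects are "identified as immunocompromised if they had ≥ 1 hospitalization or ≥ 2 outpatient visits on separate dates with an ICD-10-CM code" for an IC condition, or on use of specified immunosuppressive drugs, in the 12-month baseline period. On treatment it says: "The IC case definition will incorporate 8 groups based on clinical diagnoses only". The rheumatologic or other inflammatory group is the fifth of these eight. Medication is a condition of entry only for hematologic malignancy and the two drug-only groups.

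Annex 3 gives the codes for the fifth group. The relevant rows are:

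- "Rheumatoid arthritis/inflammatory polyarthropathy M05-M14"
- "Crystal arthropathies M11"
- "Arthropathy with infection M12.9; M01.X0; M02.10"
- "Allergic alveolitis/pneumonitis NOS T78.40; J67.9"
- "Enteritis and colitis K50-K52"

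None of these rows carries a subcode exclusion. The kidney block of the same annex also lists M10.3x, which lies inside M05-M14.

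Section 8.2.1 splits the diagnosis groups by more than 14 days of immunosuppressive use, and moves anyone who meets two groups into a group for more than one IC condition. Section 8.7 describes the IC and non-IC cohorts, reports a risk difference between them, and estimates VE for all IC subjects and by group. It names the IC case definition as something a sensitivity analysis may vary, but specifies no alternative.

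**The concern.** Section 6 gives the purpose: to learn which IC conditions predispose people to reduced VE. That needs an IC label that marks impaired immunity. Three features of the fifth group work against it.

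- T78.40 and M12.9 do not describe the condition named in their rows.
- The unrestricted arthritis range takes in gout and other arthropathies that do not by themselves indicate immunocompromise.
- With no treatment requirement, nothing later in the algorithm removes these subjects.

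At stake are the pooled IC breakthrough rate (Aim 2), the description of breakthrough cases (Aim 3), the IC versus non-IC risk difference, and the exploratory VE for the pooled cohort and this group. Classification between groups is also affected: an M10.3x code meets both the rheumatologic and the kidney definitions, so that code alone can move a subject into the group for more than one IC condition.

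**Working it through.** The plan states no share, event rate or sample size for this group, so there is no figure to reproduce. The check has two parts.

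**1. Which codes qualify.** M05-M14 expands to M05, M06, M07, M08, M09, M10, M11, M12, M13 and M14. M10 to M13 are therefore all included, and the separate M11 and M12.9 entries repeat codes already inside the range. The meanings of M10 (gout), M12.9, M13, T78.40 and K52 (other non-infective gastroenteritis and colitis) come from ICD-10-CM, the coding standard the protocol uses. The annex does not print them.

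**2. Effect on the contrast.** Assumed inputs, none of them in the documents:

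- RR: the true IC to non-IC breakthrough rate ratio, set at 3.
- f: the share of labelled IC subjects who qualify only through the disputed codes.
- k: the breakthrough rate of those subjects relative to non-IC.

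Observed ratio = (1 − f) × RR + f × k.

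With k = 1:

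| f | Observed ratio |
|---|---|
| 10% | 0.9 × 3 + 0.1 × 1 = 2.8 |
| 20% | 0.8 × 3 + 0.2 × 1 = 2.6 |
| 30% | 0.7 × 3 + 0.3 × 1 = 2.4 |
| 50% | 0.5 × 3 + 0.5 × 1 = 2.0 |

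In this case the excess (RR − 1, or the rate difference) shrinks by exactly the fraction f.

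With f = 30% and k varied:

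| k | Observed ratio |
|---|---|
| 1 | 2.1 + 0.3 = 2.4 |
| 1.5 | 2.1 + 0.45 = 2.55 |
| 2 | 2.1 + 0.6 = 2.7 |
| 3 | 2.1 + 0.9 = 3.0 (no dilution) |
| 4 | 2.1 + 1.2 = 3.3 (contrast grows) |

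**Effect on VE.** Assume a true VE of 70% in IC and 90% in non-IC subjects, added subjects with the non-IC VE, and equal unvaccinated risk and equal coverage in both. At f = 30% the mixed VE is 0.7 × 70% + 0.3 × 90% = 76%. The Section 8.7 formula agrees. With PV = 0.5 the vaccinated-to-unvaccinated risk ratio is 0.7 × 0.3 + 0.3 × 0.1 = 0.24. Then PCV = 0.12 / 0.62 = 0.1935, and VE = (0.5 − 0.1935) / (0.5 × 0.8065) = 76%.

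**The case against.** Much of the opposing case is sound.

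- A reader might infer that all these rows are mislabelled. They are not. The K50-K52 row is labelled as enteritis and colitis, which K52 fits; its problem is breadth. M11 matches its own row. For M05-M14 the label can be argued either way. The firmer objection is that gout and unspecified arthritis do not indicate immunocompromise. Listing M11 and M12.9 twice changes no one's status.
- A reader might infer that the added patients carry ordinary risk, so that the contrast must shrink. Nothing in the documents shows their breakthrough rate. If they are older and sicker, dilution could be blunted or reversed, as the rows for k = 3 and k = 4 show.
- A reader might infer that the group should be rewritten wholesale, with all of K52 dropped and M33, M34, M35.0 and M45 added. Those are clinical judgements on which experts may differ. Section 8.2.1 does not name these codes among its modifications to the source algorithm, so they may be inherited; that cannot be checked here.
- The plan has safeguards: the two-visit rule, the treated stratum, reporting by group, and an acknowledgement in Section 8.9 that the accuracy of the modified algorithm is unknown. The study is mainly descriptive and VE is exploratory.

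The safeguards help only in part. The two-visit rule screens out stray codes, not recurrent gout. The treated stratum is cleaner, but the pooled IC cohort and the fifth group overall still include the untreated. The sensitivity analysis has no defined content. Section 8.9 mentions neither these codes nor the likely direction of error.

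**Conclusion.** The point stands as a correctable flaw in the code list. T78.40 and M12.9 do not fit their rows. The unrestricted M05-M14 range lets gout and unspecified arthritis confer IC status without treatment. M10.3x can meet two groups at once.

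Dilution of the IC contrast and a raised IC VE are the expected direction, on the condition that the added subjects' breakthrough rate is below that of truly IC subjects. With an assumed true ratio of 3 and an assumed 30% share, the observed ratio runs from 2.4 (non-IC rate) through 2.7 (twice that rate) to 3.0 (three times, no effect). The actual share and rate are not in the documents, but both can be counted from the extract. The documents do not support any statement that the bias is certain or of known size.

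**What to change.** In the primary list in Annex 3:

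- Delete T78.40 and keep J67.9.
- Delete M12.9.
- Limit the rheumatoid arthritis/inflammatory polyarthropathy row to M05-M09, so that gout codes alone no longer confer membership. This also ends the double listing of M10.3x. M11 would still enter through its own row, so the sponsor should state whether that is intended.

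In Section 8.7, give the IC case definition sensitivity analysis named content:

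- (a) the list as it now stands;
- (b) a narrower list that also restricts K52, with the omitted codes M33, M34, M35.0 and M45 put to the clinical experts for review.

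Report the number of subjects who qualify only through the disputed codes, by code, for the pooled IC cohort and for this group. Their breakthrough rate would show directly whether dilution occurred.

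The cost is a code-list edit, a rerun on existing data, a somewhat smaller IC cohort, and a possible departure from the source list, which is kept as analysis (a).

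### Annex 3 codes leukocyte adhesion deficiency as the stem D72 but gives the same descriptor D72.0 elsewhere, and D71, D72.0 and D72.89 each fall in two IC groups

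*Combined protocol and SAP*

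**What the plan says.** Section 8.2.1 builds the IC cohort from claims. A subject enters a diagnosis-based group with one hospitalization, or outpatient visits on two separate dates, carrying an "ICD-10-CM code on a healthcare claim indicating an IC condition" in the 12-month baseline. Primary immunodeficiency is one of the eight groups entered on diagnosis alone; drug use only stratifies within it. The groups are mutually exclusive, and anyone who meets the criteria for more than one goes to the 12th group, >1 IC condition.

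Annex 3 supplies the codes. Under Primary Immunodeficiency:
- Leukocyte adhesion deficiency is coded "D72: Genetic anomalies of leukocytes".
- Myeloperoxidase deficiency is coded D72.89.
- Chronic granulomatous disease is coded D71.

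Under Other immune conditions the Annex prints "Genetic anomalies of leukocytes D72.0", "Decreased leukocyte count D72.81", "Leukocyte disease NEC D72.89" and "Leukocyte disease NOS D72.9", and gives D71 to functional disorders of neutrophils.

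Section 8.7 reports breakthrough incidence and exploratory VE for each IC group, and compares the IC cohort with the non-IC cohort.

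**The concern.** The same descriptor carries two different codes in one annex: a three-character category in one block and a single subcode of it in the other. The wider code sits in the list that defines the cohort, so it decides who is IC and in which group. A literal implementation would admit subjects whose codes the row does not describe. It would also change the group of subjects whose codes the Annex has already placed elsewhere.

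The double listing is a second fault. A subject with a single diagnosis code can satisfy two groups at once and be reported as having more than one IC condition. At stake are the content of the Primary Immunodeficiency, Other immune conditions and >1 IC condition subgroups and, to an unknown and possibly small extent, the boundary between IC and non-IC.

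**Working it through.** No figure in the plan bears on this point, so there is nothing to reproduce. The check applies the Annex 3 codes and the section 8.2.1 grouping rules to each code.

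**Step 1: how a bare stem is read.** Annex 3 writes D70, D86 and D89 without decimals for whole categories. It also defines organ transplant status as Z94 with Z94.81 taken out, an exception that is needed only if the bare stem includes its subcodes. By that convention D72 means every code beginning D72.

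**Step 2: assign each code.** Each code was matched by prefix against the two blocks, once with the row as printed and once with D72.0. A code that matches both blocks goes to >1 IC condition. The subject is taken to have met the claims rule and to carry no other IC code or qualifying drug use.

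| Code | Row as printed (D72) | Row as D72.0 |
|---|---|---|
| D72.1x, D72.82x (in no other row) | Primary immunodeficiency | Non-IC |
| D72.81 | >1 IC condition | Other immune conditions |
| D72.9 | >1 IC condition | Other immune conditions |
| D72.0 | >1 IC condition | >1 IC condition |
| D72.89 | >1 IC condition | >1 IC condition |
| D71 | >1 IC condition | >1 IC condition |

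The documents do not say what D72.1x and D72.82x denote. That they are eosinophilia and raised white-cell count is an assumption taken from ICD-10-CM.

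**Step 3: read the table.** As printed, the row leaves nobody coded only D72.0 in the Primary Immunodeficiency group, because D72.0 also matches Other immune conditions. The only subjects whom this row alone places in the group are those with subcodes that no row names. Changing D72 to D72.0 removes them and returns D72.81 and D72.9 to Other immune conditions. It does not touch the last three lines, where one code still counts as two conditions.

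**Step 4: illustrate dilution.** The documents give no code frequencies. Let f be the assumed share of the group's person-time from subjects who are not truly IC and who have the non-IC breakthrough rate. Let RR be the true rate ratio against non-IC. Then the observed ratio is (1 − f) × RR + f.

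| f | RR = 1.5 | RR = 2 | RR = 3 |
|---|---|---|---|
| 0.1 | 1.45 | 1.9 | 2.8 |
| 0.5 | 1.25 | 1.5 | 2.0 |
| 0.9 | 1.05 | 1.1 | 1.2 |

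For example, with f = 0.5 and RR = 2: 0.5 × 2 + 0.5 = 1.5. Both f and RR are assumed; nothing in the plan favours one line over another.

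**The case against.** The best defence is that this is a dropped .0. The cell gives a code, a colon and a descriptor, as the myeloperoxidase row does with "D72.89: Other specific disorders of White Blood Cells (WBCs", and the descriptor is the Annex's own label for D72.0. A careful programmer might therefore use D72.0. That is plausible, so the whole category cannot be called the settled intent. It does not remove the problem: the printed code and its descriptor disagree, the Annex's convention favours the wide reading, and nothing tells the programmer which to follow.

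A second defence is that every other D72 code the Annex names is already IC under Other immune conditions. For those codes the stem moves nobody from non-IC to IC. This is correct. Movement across that boundary comes only from subcodes the Annex does not name, and their clinical meaning is outside the documents. The misrouting to >1 IC condition, by contrast, follows from the documents alone.

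A third defence is that section 8.7 plans sensitivity analyses that vary the IC case definition, and section 8.9 admits that the effect of the modifications on accuracy cannot be assessed. Neither specifies a check of these codes, and neither corrects them. The sensitivity of 87.4% and specificity of 97.6% quoted there belong to the unmodified algorithm, and adding primary immunodeficiencies is one of the modifications.

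**Conclusion.** The point stands as an internal contradiction in a cohort-defining list, together with a double listing that makes one code count as two conditions. Both follow from Annex 3 and section 8.2.1. Figure 1 is not reproduced in the text available and could not be checked.

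The size cannot be computed from the documents. The dilution figures are illustrations under assumed shares, and they concern one of 12 subgroups.

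A reader might infer more, and the documents do not support it:
- **That a raised white-cell count makes a subject IC.** A coded diagnosis meeting the claims rule is needed, and the meaning of the unnamed subcodes is an assumption.
- **That the Primary Immunodeficiency results would mainly describe such subjects.** This depends on frequencies the plan does not give. Any of these subjects with a code from a second group would leave for >1 IC condition.
- **That the IC versus non-IC comparison is materially biased.** No estimate of that is possible here.
- **That T78.40, in the allergic alveolitis row, is the same kind of error.** No other Annex entry conflicts with it, so the documents show no contradiction there.

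**What to change.** In Annex 3, replace D72 with D72.0 in the leukocyte adhesion deficiency row. Then assign D71, D72.0 and D72.89 to one group each. Alternatively, add to section 8.2.1 a rule that a single code cannot count as two conditions, and state which group takes precedence. The first edit alone is not enough, because D72.0 would then be printed in both blocks and would still send the subject to >1 IC condition. If the sponsor does intend the whole D72 category, the row's descriptor should say so and the overlap with Other immune conditions should be resolved.

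The cost is a few code-list edits and a re-run. Subjects who qualify only through D72 subcodes named in no other row become non-IC, so the overall IC cohort may shrink slightly. Subjects with only D72.81 or D72.9 move from >1 IC condition to Other immune conditions. Counting subjects by qualifying D72 subcode in the same run would show how much the change matters.
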